19.4 Exploratory

Objective tumor response rates at 10-12 weeks will be summarized with a sample proportion and corresponding 95% confidence interval. Time-to-event endpoints will be examined using a Cox regression model with a factors for I-PDT (yes/no), standard-of-care type (chemotherapy, targeted therapy, immunotherapy) and an interaction term. Survival curves will be estimated per group using Kaplan-Meier estimates. It is assumed a priori that any drop out times will be non-informative in terms of the censoring mechanism.

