1.2 Exploratory Objectives

• To assess the objective tumor response rate.

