8.0 Study Endpoints

8.1 Primary Endpoints

Phase 1:

o The safety will be determined by recording the occurrence of AE during the first 30 days post final I-PDT day, using the revised NCI Common Terminology Criteria for Adverse Events (CTCAE) version 5.0.

Exploratory Endpoint

Objective target tumor response rates will be assessed according to RECIST v1.1 at 12 ± 2 weeks post I-PDT as described in section 16.2.

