9.0 Study Design

All participants will meet the inclusion and exclusion criteria summarized in Section 3.1 and Section 3.2 prior to taking part in this study.

This study will recruit subjects with HNC who failed to respond to standard therapy and are not candidates for salvage surgery or radiation therapy including re-irradiation. These HNC subjects would otherwise receive SoC chemotherapy, targeted therapy or potentially immunotherapy as first line palliative care treatment options.

All participants will receive I-PDT. All participants will have a standard diagnostic head and neck scan with CT or MRI, with or without contrast. Participants will be followed according to the 2018-NCCN follow-up guidelines (63; Appendix H) for patients with advanced HNC (https://www.nccn.org/professionals/physician_gls/pdf/head-and-neck.pdf). The study related visits would be up to 2 years, thus every 1-3 months in the first year, and every 2-6 months in the second year. The routine clinical follow up will be up to 5 years. The study schema is shown in

[figure not shown]
[figure not shown]

Figure 3 Study Schema

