12.0 Withdrawal of Subjects

Subject Withdrawal

The subject will be withdrawn from the study as described in Section 10.5 and if:

- The I-PDT can't be administered.
- The patient would become hemodynamically unstable during I-PDT.

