14.0 Potential Benefits to Subjects

For subjects that will have partial or complete response to I-PDT, the potential benefits include reduction in tumor related side effects (such as bleeding, pain, and dysphagia). Subjects that do not respond to I-PDT may not benefit from this treatment. In addition it has been shown, in other diseases sites, that PDT can improve OS and PFS when added to SoC therapy. Thus, it is possible that subjects that will respond to the experimental arm (I-PDT + SoC) will have increased OS and PFS. There is no guarantee of the outcome nor is it possible to predict whether or not the subject will respond to porfimer sodium-mediated I-PDT.

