16.2 Target Lesions

The target lesions will be the locally advanced HNC that were treated with I-PDT or the ones that were identified by the principal investigator (or treating physician) as locally advanced and were treated with SoC therapy. Tumors measurements will take place 10-12 weeks after I-PDT or the first SoC in the control ram. Change in the target tumor size will be determine using the methods described in RECIST v1.1 (62). CT with contrast or MRI (when CT is not possible) will be used to determine change in tumor size. The objective response of the target tumor will be determined following these criteria:

- Complete Response (CR): Disappearance of all target lesions. Any lymph nodes must have a reduction in short axis to < 10 mm.
- Partial Response (PR): At least a 30% decrease in the sum of diameters of target lesions, taking as reference the baseline sum diameters. A biopsy will be taken from the suspected lesions for histological confirmation.
- **Progressive Disease (PD):** At least a 20% increase in the diameters of target lesions, taking as references the smallest sum on study (this includes the baseline sum if that is the smallest on study). In addition to the relative increase of 20%, the sum must also demonstrate an absolute increase of at least 5 mm.

• **Stable Disease (SD):** Neither, sufficient shrinkage to qualify for PR nor, sufficient increase to qualify for PD, taking as reference the smallest sum diameters while on study, the response will be listed with stable disease. In this case, a biopsy will be taken from the suspected lesion for histological confirmation.

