Fresh Tissue Tumor Biopsy ^F	X			X			
Standard Imaging of the head and neck with CT or MRI ^G	XH						XI
Treatment planning	X						
Porfimer Sodium administration and Vital Signs		X^{J}					
Intraoperative Ultrasound ^Q			X				
If possible, intraoperative CT or other clinically approved radiological imaging			X ^K				
Interstitial PDT (I-PDT)			$X^{L, Li}$				
Concomitant Medications	X ^M		X				
Standard of care (SoC) chemotherapy, targeted therapy or potentially immunotherapy as first line palliative care treatment options					X ^N		
Adverse Events ^O	X ^{Oi}		X	X	X	X	

Notes:

^{*} The I-PDT procedure is termed a "course". As per later Section 10.4, study participants may have up to 3 I-PDT courses per physician's discretion, at least 30 days from the previous illumination procedure.

- ** NOTE: 2nd and 3rd I-PDT courses are per the physician's discretion as per Section 10.4, 2nd and 3rd I-PDT courses are not required for all study participants. If it is decided participants should receive all 3 I-PDT courses, items from "Repeat of Initial Tests and Procedures" until the completion of I-week Post treatment" are completed twice before the Clinic Visit and start of Standard of Care chemotherapy.
 - A. Performed within 4 weeks prior to 2nd and 3rd I-PDT courses. Since there may be up to three I-PDT courses, at least 30 days apart (see Section 10.4) per the physician's discretion, the initial procedures, exams, or tests may be completed up to two more times based on the individual participant's study treatment regimen. Research blood draws, standard imaging of head and neck with CT or MRI, and treatment planning for later I-PDT courses are per physician's discretion.
 - B. Temperature, heart rate, respiratory rate, blood pressure, and body weight. Refer to Section 11.2.
 - C. Hematology (i.e., CBC (with auto differential), ANC, and platelets). Refer to Section 11.2.
 - D. Chemistry (i.e., AST, ALT, total bilirubin, alkaline phosphatase, creatinine, potassium, glucose, and calcium). Refer to Section 11.2.
 - E. This is optional. Research blood draws for any 2nd and 3rd I-PDT courses (all timepoints) are per the physician's discretion. Refer to immune markers Section 11.8 (1 green top tube).

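### The I-PDT and interaction terms in the Section 19.4 Cox model cannot be estimated because everyone receives I-PDT, and the response scan has no single anchor date

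*Combined protocol and SAP*

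**What the plan says.** **Time-to-event model.** Section 19.4: "Time-to-event endpoints will be examined using a Cox regression model with a factors for I-PDT (yes/no"), plus SoC type (chemotherapy, targeted therapy, immunotherapy) and an interaction. Kaplan-Meier curves are to be drawn per group, with the groups undefined. Section 9.0: "All participants will receive I-PDT". Section 12.0 lists among the reasons for withdrawal: "The I-PDT can't be administered". The only exploratory objective, in Section 1.2, is "To assess the objective tumor response rate", and Section 8 names no time-to-event endpoint. Section 14.0 still speaks of a two-arm trial: "subjects that will respond to the experimental arm (I-PDT + SoC) will have increased OS and PFS".

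**Response timing.**
- Section 8.1: "at 12 ± 2 weeks post I-PDT as described in section 16.2".
- Section 16.2: "Tumors measurements will take place 10-12 weeks after I-PDT or the first SoC in the control ram".
- Section 11.6: 10-12 weeks after the initial study treatment, citing 8.1.
- Section 19.4: 10-12 weeks, no starting point.
- Appendix D note 8: 10-12 weeks after SoC.
- Appendix D 1 note G: 10-12 weeks after I-PDT.
- Appendix D note 18: after an added complete treatment, tests follow the same schedule as the initial one.
- Section 10.4: up to three sessions at least 30 days apart. The date of the last course sets the scheduling of follow-up SoC; the response scan is not mentioned.

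The Appendix D 1 notes place SoC after I-PDT: when all three courses are given, the repeat procedures "are completed twice before the Clinic Visit and start of Standard of Care chemotherapy".

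**The concern.** A yes/no treatment factor needs participants in both categories, and this design has only one. The wording of 19.4 fits a controlled trial, as do the control arm in 16.2 and the experimental arm in 14.0. Left as it is, the analyst must make an unplanned choice, or software silently drops the aliased terms and returns SoC contrasts that no objective asks for.

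The scan date matters because objective response is the one exploratory endpoint that Section 8 names. With at most 12 participants, a few assessments read at different points relative to treatment can move the proportion. The anchor also determines whether SoC has begun by the time of the scan, and so whether a response can be attributed to I-PDT alone.

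**Working it through.** **Plan's own figure.** Section 4.0 gives four cohorts of 3: 4 × 3 = 12, matching the maximum in Section 19.1. No event count, hazard ratio or power is stated for the Cox model.

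**Estimability.** Let x be the I-PDT indicator, s1 and s2 the dummies for three SoC types, and x·s1, x·s2 the interactions: 1 + 2 + 2 = 5 coefficients.

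1. With x = 1 for everyone, each partial-likelihood term has exp(β·1) in the numerator and in every summand of the denominator. It cancels, so the likelihood does not depend on β. Equivalently, the variance of x in every risk set is 0, so its information is 0.
2. x·s1 = s1 and x·s2 = s2. Only the sums of each SoC coefficient and its interaction coefficient can be learned.
3. At most 2 of the 5 dimensions are identified. If only two SoC types occur, 1 is.

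Numerical check, assuming 12 participants, 4 per SoC type and all with events: the diagonal of the information matrix is 0, 2.407, 1.845, 2.407, 1.845, with rank 2. The split and event count are assumptions, but the zero and the duplicated columns do not depend on them.

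Participants with no therapeutic SoC, foreseen in Section 19.3 and Appendix D note 14, have no category. Adding a fourth level would give 1 + 3 + 3 = 7 coefficients with rank at most 3.

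**Window width, one unsplit course.** 12 ± 2 weeks is days 70-98; 10-12 weeks is days 70-84. The I-PDT-anchored passages, and 11.6 if the initial treatment is taken as that course, all allow days 70-84. Only a scan on days 85-98 meets 8.1 but not the others. Note 8 counts from SoC, whose start relative to I-PDT is not fixed, and is undefined if no SoC is given.

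**Anchor, repeat courses.** Days are counted from the first I-PDT, at the 30-day minimum of 10.4. The last-course window is 70 to 84 days after day 30 × (number of courses − 1).

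| Courses | From first course | From last course | Overlap |
|---|---|---|---|
| 1 | 70-84 | 70-84 | full |
| 2 | 70-84 | 100-114 | none |
| 3 | 70-84 | 130-144 | none |

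With the 8.1 width, the last-course windows become days 100-128 and 130-158, still without overlap.

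**Anchor within one course.** Appendix D note 16 and Appendix D 1 note P allow split sessions up to 14 days after the first. A scan 10-12 weeks after the first session is then 8-10 weeks after a session on day 14. Note 17 allows light-only treatment within 2-3 weeks of the drug, which is given about 2 days before light. Three weeks after drug is about day 21 − 2 = 19 from first light, so the scan falls (70 − 19)/7 = 7.3 to (84 − 19)/7 = 9.3 weeks after it. No passage says which session starts the clock.

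**The case against.** **On the model.** One could code withdrawn participants as no I-PDT, or point to Section 2.6.2, which mentions patients not treated with PDT. Neither helps. Withdrawn participants would be a handful defined by failure to receive treatment, and 2.6.2 concerns a tumour-tissue comparison, not survival. A time-dependent I-PDT covariate could vary, but none is planned.

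A reader might infer that the whole Cox model is void. It is not: the SoC-type contrasts are estimable in principle, though in at most 12 participants and for a factor arising after I-PDT. A reader might also infer that the Kaplan-Meier curves are meant to compare I-PDT with none. Section 19.4 says only per group, so the fair criticism is that the group is undefined.

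**On timing.** Repeat courses are optional and at the physician's discretion, and for one unsplit course the passages agree at 10-12 weeks apart from note 8. That stands, and it limits the problem. The last-course sentence in 10.4 might be read as settling the anchor. It is the nearest thing to a rule, but it concerns follow-up SoC and does not name the scan, while 11.6 points to the initial treatment.

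It is tempting to put a figure on the SoC anchor by equating the Appendix D Clinic Visit (Day 1 of SoC) with the Section 11.5 visit at 1 to 4 weeks. Appendix D also has a 1-week post-treatment column that fits 11.5 equally well, so the documents do not support a figure.

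**On course spacing.** The 30-day minimum in 10.4 and the 6-week minimum in the Appendix D header are nested rather than mutually exclusive. They still differ, but this is a side issue here.

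**Conclusion.** Both parts hold. The non-estimability of the I-PDT and interaction terms is structural: no sample size, event count or SoC mix repairs it. The figure of 5 coefficients with rank at most 2 assumes that everyone falls in one of the three listed SoC types.

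The response anchor is contradictory in general, but how much depends on the participant. For one unsplit course the conflict is confined to Appendix D note 8, plus a minor difference in width. For two or three courses at the 30-day minimum, the first-course and last-course windows do not overlap. That comparison takes post I-PDT to mean after the last course, a reading 10.4 makes plausible but no passage states for the scan.

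A reader might infer that the trial's main conclusion is at risk. It is not: the primary safety objective uses neither the Cox model nor the response scan. The stakes are limited to exploratory analyses.

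**What to change.** 1. Delete the Cox model from 19.4, and remove the control-arm wording in 16.2 and the experimental-arm wording in 14.0.
2. Either drop the time-to-event analysis, or name the endpoint and its time origin in Section 8 and give a descriptive single-arm Kaplan-Meier estimate with a 95% confidence interval. If it is kept, first confirm that the follow-up data support it: the explicit death-recording rule in 10.5 covers only 30 days after treatment.
3. Reconcile 8.1, 10.4, 11.6, 16.2, 19.4, Appendix D notes 8 and 18 and Appendix D 1 note G to one window and one I-PDT anchor, stating which course and which session counts. Report how many participants had started SoC before the scan.
4. Reconcile the repeat-course spacings in 10.4 and the Appendix D header. This review takes no position on which applies.

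The cost is wording changes, with no extra participants or procedures. The exception is a retained time-to-event endpoint, which may require additional follow-up data.

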7.0 Study Timelines

A maximum of 12 participants at Roswell Park will be enrolled. Accrual is expected to take 5 years, with follow-up for 24 months from the start of investigational treatment.

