11.5 Evaluations Performed at 1st Post-Operative Clinic Visit

This visit will be scheduled 1 to 4 weeks post I-PDT and will include:

- Physical examination, including vital signs (i.e., temperature, heart rate, respiratory rate, blood pressure, body weight, and pain assessment using a verbal score of 0-10)
- Hematology (i.e., CBC (with auto differential), ANC, and platelets)
- Chemistry (i.e., AST, ALT, total bilirubin, alkaline phosphatase, creatinine, potassium, glucose, and calcium)
- ECOG Performance Status
- Adverse events
- UW QoLQ v4
- Research blood draws (Optional) #

Performed as per PI discretion if later I-PDT courses are deemed necessary as per Section 10.4.

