19.3 Safety Analysis

The safety will be determined by recording the occurrence of SAE during the first 30 days post first SOC treatment day (or last I-PDT day if no therapeutic SOC is given) using the revised NCI Common Terminology Criteria for Adverse Events (CTCAE) version 5.0. Sequential boundaries will be used to monitor the SAE rate (64). The accrual will be halted if excessive numbers of SAEs are seen.

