Appendix D Schedule of Procedures and Observations if Only I-PDT Course is Necessary

Evaluation	Baseline ¹	Pre- Operative	Day of Treatment	Day 1 Post Treatment	1-week Post- treatment	Optional I-PDT Course 2 Within 2-3 Weeks of Day 0 ¹⁷	Clinic Visit ^{2,2a}	30- Day Post I- PDT ¹⁴	Optional I-PDT Treatment additional 2 or 3 At least 6 Weeks after last I-PDT Session ¹⁸	Follow- Up
Informed Consent	X									
Medical History	X								X	
Physical Exam/ Vital signs & pain assessment using a verbal score 0-10 ³	X				X		X	X	X	X
Hematology ⁴ and Chemistry ⁵	X				X		X	X	X	
Research Blood Draws ⁶			X		X		X	X	X	
Pregnancy Test (Urine)	X								X	
ECOG Performance Status	X		X		X		X	X	X	X
UW-QoLQ v. 4 ¹⁵	X				X		X	X	X	X
Standard Imaging of the head and neck with CT or MRI, for RECIST v11.1	X ⁷								X	X8
Treatment planning	X								X	
Porfimer Sodium administration and Vital Signs		X ⁹							X	
Intraoperative Ultrasound			X						X	
If possible, intraoperative CT or other clinically approved radiological imaging			X^{10}			X ¹⁰			X^{10}	
Interstitial PDT (I-PDT) 16			X^{11}			X ¹¹			X ¹¹	
Concomitant Medications	X ¹²		X							
Adverse Events ¹³			X		X		X	X		

Notes:

- * The I-PDT procedure is termed a "course".
 - 1. Performed within 8 weeks prior to porfimer sodium.
 - Performed at Day 1 of SOC therapy.
 If later 2nd and 3rd I-PDT courses are deemed necessary per the physician (see Section 10.4), please refer to Appendix D 1 for treatment, procedure, and test scheduling.
 - 3. Temperature, heart rate, respiratory rate, blood pressure, body weight and, height, Height collected at baseline only. Refer to Section 11.2.
 - 4. Hematology (i.e., CBC (with auto differential), ANC, and platelets). Refer to Section 11.2.
 - 5. Chemistry (i.e., AST, ALT, total bilirubin, alkaline phosphatase, creatinine, potassium, glucose, and calcium). Refer to Section 11.2.
 - 6. This is optional. Refer to immune markers Section 11.8 (1, 10 mL green-top tube).
 - 7. Standard tumor staging performed within 4 weeks, and at least 14 business days prior to I-PDT. If possible, the imaging will include temporary fiducial markers that will be affixed to skin. Refer to Section 11.2.
 - 8. CT scans at 10 to 12 weeks post SOC therapy and as clinically indicated following the NCNN 2018 guidelines.
 - 9. Infusion will occur 48 hours ± 8 h prior to illumination. Vitals are to be taken immediately after injection and after 15 minutes.

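### Section 19.4 uses standard-of-care (SoC) type, a treatment begun only after I-PDT, as a fixed Cox factor and probably as the Kaplan-Meier grouping, so participants who die before SoC or never start it drop out

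*Combined protocol and SAP*

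**What the plan says.** - **Model and curves (19.4).** The Cox model has an I-PDT (yes/no) factor, then "standard-of-care type (chemotherapy, targeted therapy, immunotherapy) and an interaction term. Survival curves will be estimated per group using Kaplan-Meier estimates". The SoC factor has three levels and none for participants without SoC. No endpoint, time zero, landmark, delayed entry or time-dependent covariate is given. The only stated assumption is that drop-out is non-informative.
- **I-PDT (9.0).** "All participants will receive I-PDT".
- **Timing of SoC.** Note 2 of Appendix D, attached to the Clinic Visit column, reads "Performed at Day 1 of SOC therapy". Section 11.5 says of the first post-operative clinic visit: "This visit will be scheduled 1 to 4 weeks post I-PDT and will include". For repeat courses, the ** note of Appendix D 1 says the I-PDT steps "are completed twice before the Clinic Visit and start of Standard of Care chemotherapy".
- **SoC may not happen (19.3).** The safety window allows for this case: "or last I-PDT day if no therapeutic SOC is given".
- **Baseline (11.2).** The list of baseline evaluations contains no intended SoC type.
- **Follow-up origin (7.0).** The only one stated is "follow-up for 24 months from the start of investigational treatment".

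**The concern.** With the I-PDT factor constant, that term and its interaction cannot be estimated. What remains of the model is SoC type. Nothing in the plan fixes SoC type at entry, so as written it can come only from treatment actually started, after time on study has already passed.

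Two effects follow. First, selection: a participant who dies, deteriorates or otherwise never starts SoC has no level of the factor and no SoC curve. Second, guaranteed time: if the clock starts at I-PDT, nobody in a SoC group can die between I-PDT and the start of SoC. Both make survival by SoC group look better than survival in all treated participants. Deleting the inestimable I-PDT term does not cure this; it leaves exactly this analysis in place.

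**Working it through.** **The plan's own figure.** Maximum N: four cohorts of 3 = 12, and two dose levels × up to 6 = 12, so Section 4.0 reproduces. No event count, power or hazard ratio is stated for survival, so the rest is illustration.

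**Inputs**
- Median survival m: 7 and 10.3 months, the first-line trial figures quoted in 2.1. The median for this population is not given, so this is an assumed range.
- Delay d from first I-PDT to SoC after one course: 7 to 28 days (11.5 read with note 2 of Appendix D).
- Delay after three courses at the 30-day minimum spacing in 10.4: 60 + 7 = 67 to 60 + 28 = 88 days.
- One month = 30.4375 days; constant hazard.

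**Formulas**
- P(death before SoC) = 1 − exp(−ln 2 × d / m).
- Expected number = 12 × P; chance of at least one = 1 − (1 − P)^12.
- Median counted from first I-PDT among those who reach SoC = m + d (constant hazard has no memory).

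Example, m = 7 months = 213.06 days, d = 28: P = 1 − exp(−0.6931 × 28 / 213.06) = 1 − exp(−0.0911) = 0.087; 12 × 0.087 = 1.04; apparent median = 7 + 28/30.4375 = 7.92 months.

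| m (months) | d (days) | P | Expected of 12 | P(at least 1) | Apparent median (months) |
|---|---|---|---|---|---|
| 7 | 7 | 0.023 | 0.27 | 0.24 | 7.23 |
| 7 | 28 | 0.087 | 1.04 | 0.66 | 7.92 |
| 7 | 67 | 0.196 | 2.35 | 0.93 | 9.20 |
| 7 | 88 | 0.249 | 2.99 | 0.97 | 9.89 |
| 10.3 | 7 | 0.015 | 0.18 | 0.17 | 10.53 |
| 10.3 | 28 | 0.060 | 0.72 | 0.52 | 11.22 |
| 10.3 | 67 | 0.138 | 1.65 | 0.83 | 12.50 |
| 10.3 | 88 | 0.177 | 2.12 | 0.90 | 13.19 |

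The 67- and 88-day rows describe a trial in which all 12 participants have three courses.

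**Choice of clock.** If time is counted from first SoC, the median stays at m and the guaranteed time disappears. The deaths in the fourth column are still missing, and participants who never start SoC have no time zero.

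**Hazard ratio between SoC types.** Large null simulations (40,000 participants before exclusions, 7-month median, 24-month censoring, no true difference) gave these ratios for the later-starting type against the earlier:

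| Delays (days) | Fixed factor | Delayed entry at SoC start |
|---|---|---|
| 28 vs 28 | 1.00 | 1.01 |
| 7 vs 28 | 0.93 | 1.01 |
| 30 vs 90 | 0.80 | 0.99 |
| 7 vs 90 | 0.77 | 1.01 |

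The comparison between types is therefore biased only to the extent that start delays differ.

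**Adding a fourth level for no SoC is not a cure.** With the same null set-up, SoC at day 28 and an assumed 10% or 30% never treated for other reasons, the hazard ratio for SoC against none was 0.51 or 0.76, although the truth is 1.

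**The case against.** The strongest reply is that 19.4 is too loosely written to convict.

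- **Time zero.** A reader might infer that every curve certainly carries guaranteed survival time. The documents do not go that far. Section 7.0 gives the length of follow-up, not the origin of a survival analysis, and 16.2, 19.3 and note 8 of Appendix D count some intervals from SoC. This stands, so the guaranteed time is conditional on an I-PDT clock. The omission of deaths before SoC is not.
- **Grouping.** The group is undefined and could mean dose level, or the I-PDT factor, which would give a single curve. SoC type remains the only factor in that model able to vary, so it is the likeliest reading, but it is an inference.
- **Intended SoC.** Section 9.0 names the options patients would otherwise receive, so a planned type could be fixed at entry. Section 11.2 does not collect one.
- **Start dates.** Day 7 to 28 joins two passages. The documents give no rule for starting SoC, and a note to Appendix D 1 puts Phase 1 patients off treatment 30 days after the last I-PDT. The delays are assumptions.
- **Size.** It is tempting to say that up to 3 of 12 would be lost. That needs three courses for everyone, and 10.4 and Appendix D 1 make repeat courses discretionary. Constant hazard with a 7-month median also implies 45% dead by 6 months, while inclusion criterion 5 asks for a life expectancy of at least 6 months, so early deaths may be overstated.
- **Consequence.** One might suppose that a Phase 2 trial would build on these curves. The documents do not say so: what passes to Phase 2 is the light irradiance (1.1), and survival is neither an objective nor a listed endpoint.

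It is also true that absence of SoC need not mean early death. For a progression endpoint, reaching SoC guarantees being alive, not being progression-free.

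**Conclusion.** The point holds in limited form. Followed as written, with SoC type taken from treatment received, 19.4 leaves deaths before SoC and non-starters out of the Cox factor and, on the likely reading, out of the curves. That is so under either clock. On a clock from the start of investigational treatment, the SoC curves are also raised by guaranteed time.

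For one course, the illustration gives 2-9% dying before SoC (0.2 to 1.0 of 12) and a median raised by 0.2 to 0.9 months. About 2 to 3 of 12 is the upper bound at 30-day spacing, and only if all participants had three courses. These figures rest on exponential survival, medians borrowed from the background section and assumed SoC start days. The direction of the effect on an I-PDT clock does not depend on them.

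A reader should not infer that the hazard ratio between SoC types is necessarily distorted: with equal delays it is not. In an exploratory analysis of at most 12 participants the priority is modest, but the text should be corrected.

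**What to change.** In 19.4:

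1. Remove the I-PDT and interaction terms, which cannot be estimated, and remove SoC type as a fixed Cox factor and as the Kaplan-Meier grouping.
2. Name the time-to-event endpoint and report one Kaplan-Meier curve with time zero at first I-PDT for all treated participants, including those who never start SoC.
3. If survival by SoC is still wanted, keep it descriptive. Set one fixed landmark day in advance, counted from the **first** I-PDT. Class participants alive at that day by SoC started by then, with a none/not-yet category, and count time from the landmark. Report the number who never start SoC.

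Items 1 and 2 cost wording only and remove the bias under any reading of group or clock. Item 3 needs the type and start date of SoC for each participant. The single-course schedule in Appendix D has no row for SoC, so the sponsor should check that the case report form captures them. The landmark display omits deaths before the landmark and places participants still having repeat courses under not-yet, but all of them remain in the overall curve.
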